Number of participants with rationale	
The mean knowledge score found in heart failure patients hospitalized at the HUG and naïve to any educational program was 7.95 points out of 17 points, with a standard deviation of 2.67. A 30% difference in score improvement was chosen as the smallest

	
difference to be detected with clinical significance (i.e., a score difference of 2.39) to be detected. Assuming a study power of 80% and an alpha error of 5% (two-sided), it would be necessary to recruit a total of 80 patients (40 per group) to be able to detect such a difference between the two groups. We anticipate 10% loss to follow-up, which leads to a sample size of 90 subjects in total, or 45 per group. This sample size was calculated with STATA 17 (STATA Corporation, College Station, Texas).
 
We expect to include approximately 124 patients during the 12-month inclusion period. Indeed, 200-300 patients are hospitalized annually at the HUG in the Department of General Internal Medicine or Cardiology for heart failure with reduced LVEF, i.e., about 16-25 patients per month. Taking into account refusals to participate and patients we will not have time to include, we think we can reach 62 patients per group.

Study Intervention	
The intervention by a clinical pharmacist includes
 
 
- Targeted education on patient needs related to heart failure, heart failure medications and self-care;
 
- a pre-discharge interview to consolidate key teaching messages and prepare the patient for their discharge treatment plan;
 
- a telephone call the week of discharge to ensure pharmaceutical follow-up between hospital care and return home (continuity of care).
 

Control Intervention	
Hospitalized heart failure patients with reduced or mildly reduced LVEF who do not benefit from the pharmacist's educational intervention but do benefit from the usual standard of care.

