#### **3.2 Primary and secondary endpoints**

The primary endpoint was the level of patient knowledge by setting an improvement of at least 30% (relative gain) as the smallest gain to be detected at 1 month of hospitalization in the intervention group compared with the control group.

This value was chosen arbitrarily based on what has been found in other published research (45–56) and also based on the experience gained from other research projects conducted at the pharmacy in the field of education.

1 The level of knowledge of the patients will be measured using a knowledge score that is in the  
 2 form of a knowledge assessment questionnaire created specifically for this project (Appendix  
 3 1).

4  
 5 It assesses patients' knowledge on two topics: heart failure disease and heart failure  
 6 medications. It is composed of 17 questions, 8 of which are multiple-choice questions of  
 7 category K' (several correct answers), 6 of type A (only one correct answer) and 3 open-ended  
 8 questions (free text evaluated by keyword).

9 Six questions are related to the theme of heart failure disease and assess different elements  
 10 of knowledge such as the definition of the disease, the notion of chronicity and progression,  
 11 the symptomatology of decompensated disease, the precipitating factors of decompensation  
 12 and the correct actions to adopt in case of decompensation of the disease. The remaining 11  
 13 questions assess patients' knowledge of their heart failure medications, including the  
 14 identification of heart failure medications among all treatments, the usefulness of these  
 15 medications, the duration of treatment, the continuous adjustment of doses, the risks of non-  
 16 optimal therapeutic adherence, the adverse effects of the main classes, and the correct actions  
 17 to take in the event of the occurrence of adverse effects of these medications and of forgetting  
 18 to take them. Each correct answer is worth 1 point. The scoring or quotation of the answers  
 19 will be done in the following way:

20  
 21 Simple choice question with a dichotomous notation: Right answer 1 point and wrong answer  
 22 0 point

23  
 24 Multiple choice question with partial credit scoring 50 (PS50): score with partial reward where:  
 25 1 if all propositions correct; 0.5 if more than 50% of propositions correct; 0 points otherwise.

26  
 27 Open-ended question with partial scoring based on subjective keyword evaluation.  

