 28 For example for question n° 2: 1 point if predefined keyword present; 0,5pt if partial keyword  
 29 but general concept correct; 0 pt otherwise.

30  
 31 The final score can vary from 0 (no knowledge) to 17 points (excellent knowledge).  
 32 The questionnaire has never been used in an experimental context or for psychometric  
 33 analysis. There is no threshold to say that a patient has good knowledge or not.  
 34 It was developed by an internal pharmacist and an assistant pharmacist trained in TVE. It is  
 35 based on educational objectives derived from educational sessions with patients and meetings  
 36 with two patient partners from the HUG (Appendix 2). It was previously evaluated with them  
 37 and on three occasions with a group of hospitalized heart failure patients (10 patients per  
 38 version of the questionnaire).

39  
 40 To determine a first basic level of knowledge of the heart failure patients hospitalized at the  
 41 HUG, the final version of the questionnaire was tested with 10 patients who had not received  
 42 any educational intervention. This analysis shows that:

- 43 • The average baseline score is 7.95 pts out of 17.00pts (with a standard deviation of  
 44 2.67) or 46.76% of correct answers;
- 45 • The median score of 8.25pts out of 17.00 pts (min. 4; max. 13) or 48.53% of correct  
 46 answers.

47  
 48 In this clinical study, we wish to assess the level of knowledge of the intervention group before  
 49 the teaching interview, directly after the teaching interview, and at 1 month after the  
 50 participant's discharge from the hospital.

51 This study includes a control group in order to evaluate the real effect of the therapeutic  
 52 teaching intervention. The level of knowledge of the control group will be evaluated at inclusion  
 53 for the pre-test and at 1 month after hospitalization for the post-test.

54

1  
2 Secondary endpoints included differences in medication belief and adherence scores and the  
3 difference in the rate of unplanned care use between the two groups at 1 month post-  
4 hospitalization.

5  
6 They also focused, for the intervention group, on the difference in belief and therapeutic  
7 adherence scores between the period before the educational intervention during  
8 hospitalization and the period following this intervention, i.e., one month after hospital  
9 discharge.

10 Four additional endpoints will be assessed after the pharmaceutical intervention with the study  

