**Storage:**

The identification list of participants will be kept in a secure manner (see §8.2 data recording and source data)

For the duration of the study, the data will be stored in the CDMS, REDcap™, which can only be accessed by the investigator and a research assistant with a personal login and password.

All paper source data will be available in a dedicated study cabinet. This cabinet will be stored in the pharmacy's clinical trials office. All other source documents will be stored electronically, in the pharmacy's secure network, accessible only by the principal investigator and his/her research assistant.

Access to the database will be available to the study investigator and research assistant only during the inclusion process, but also during the data analysis phase and after the study is completed. Access will be password protected to prevent unauthorized access.

Once the data is collected and the REDCap™ database is complete, the data will first be extracted into an Excel spreadsheet. This will be stored in the pharmacy's secure network.

For the statistical analysis, the data of interest will be prepared for transfer to the statistician of the Methodological Support Unit, so that he can import them into the statistical software he will use. A do-file will be used to store all the statistics produced.

Where possible, we will store files in open archive formats, such as Word files converted to PDF-A or simple text files encoded as UTF-8 files and Excel files converted to CSV. If this is not possible, we will include information about the software used and its version number.

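### Three of the 17 primary-endpoint items are free text scored by judgement, with no named scorer and no masking; even a small arm-related scoring shift raises the false-positive rate

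*Combined protocol and SAP*

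**What the plan says.** **The items.** Section 3.2 divides the questionnaire into 8 multiple-choice questions, "6 of type A (only one correct answer) and 3 open-ended" questions. Single-choice and multiple-choice items follow fixed scoring rules. The free-text rule is "Open-ended question with partial scoring based on subjective keyword evaluation". The only worked example, for question 2, reads "1 point if predefined keyword present; 0,5pt if partial keyword", where the half-point also requires that the overall idea be right; anything else scores 0. The same section states that the questionnaire has had no experimental use and no psychometric analysis.

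**Who scores.** No section says. Table 2 (section 4.3) gives the origin of the score only as a calculation. No masked scoring, second rater or agreement check is described.

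**Who has access and what they know.**
- The Synopsis (Data privacy) and section 8.3 limit study data access to the investigator and the clinical research associate. The Storage paragraph confirms this for the database and extends it through analysis and beyond study end.
- The investigator learns the arm after consent (section 4.2), delivers the teaching (section 3.4) and may help patients with the in-hospital questionnaires (section 4.3).
- For the intervention group, the Synopsis assigns the 1-month assessment to the research associate alone. Section 3.2, however, has the e-mailed or posted questionnaires come back to the investigator, with the research assistant telephoning non-responders. I take research assistant and research associate to be the same role.
- Satisfaction is assessed in the intervention group only (section 4.3). The app questionnaires go only to intervention patients who installed the app (sections 3.2 and 4.3).
- The statistician receives prepared data (section 8.3) and has no scoring role.

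**The concern.** The half-point rule asks the scorer whether an imperfect answer shows the right idea. If the scorer knows the arm, an ambiguous answer from a taught patient may be read more generously than the same words from a control. That difference enters the primary endpoint directly and looks like a teaching effect. A positive trial would be open to the objection that the teacher marked the answers.

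The baseline adjustment in section 5.1 does not solve this. It corrects for differences in the pre-test score, not for a shift that arises when the 1-month answers are scored. The pre-test is itself collected after randomization (section 4.3), so it could also be scored with the arm known. Had the pre-test been shifted equally, ANCOVA would remove only the part given by the regression slope.

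**Working it through.** **1. Inputs.**
- Open items: 3 of 17, each worth 0, 0.5 or 1. The 0.5 step is documented for question 2; I assume it for the other two. Closed items: 8 + 6 = 14.
- Target difference: 2.39 points (Synopsis and section 5.1).
- Pilot result in 10 patients: "7.95 points out of 17 points, with a standard deviation of 2.67".
- Group sizes: 40 before loss, 45 after allowing for loss, and 62 expected (section 5.1).
- Assumption, not in the documents: a share f of open answers in one arm is scored a half-point differently because of the arm. I use f = 10%, 20% and 30%.

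**2. The plan's own sample size, to settle which SD to use.** n per group = 2 × (1.960 + 0.842)² × SD² / 2.39².
- SD = 2.67 gives 19.6, so 20 per group.
- SD = 2.67 × √2 = 3.78 gives 39.2, so 40 per group, the plan's figure. This is the SD of an unadjusted change score with no pre–post correlation, an assumption the plan does not state.
- 40 / 0.9 = 44.4, so 45 per group.

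I therefore use both SDs as a range. The basis of the 40 is a separate matter.

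**3. Size of the shift.** Shift = f × 3 items × 0.5 point.

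| Share f | Shift (points) | Share of 2.39 |
|---|---|---|
| 10% | 0.15 | 6% |
| 20% | 0.30 | 13% |
| 30% | 0.45 | 19% |
| one third (one answer per patient) | 0.50 | 21% |
| 100% | 1.50 | 63% |

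**4. False-positive rate with no true effect.** Two-sided, unadjusted two-sample t-test at 5%. SE = SD × √(2/n), and the rate is the probability that |t| exceeds its critical value when the noncentrality is shift / SE. Example with n = 45 and SD 2.67: SE = 2.67 × √(2/45) = 0.563; for a shift of 0.45 the noncentrality is 0.45 / 0.563 = 0.80, and the rate is 12.4%.

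| Shift | 45/group, SD 3.78 | 45/group, SD 2.67 | 62/group, SD 3.78 | 62/group, SD 2.67 |
|---|---|---|---|---|
| 0.15 | 5.4% | 5.8% | 5.6% | 6.1% |
| 0.30 | 6.6% | 8.2% | 7.2% | 9.5% |
| 0.45 | 8.7% | 12.4% | 10.1% | 15.4% |
| 0.50 | 9.5% | 14.2% | 11.3% | 17.9% |

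A larger sample makes a fixed bias more likely to reach significance, so recruiting 62 per group does not protect against it.

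**5. Limits of the approximation.** The planned analysis is ANCOVA with the baseline value carried forward when the 1-month score is missing. Adjustment reduces the residual SD, which raises these rates for a given shift. Carrying baseline forward dilutes a 1-month shift in proportion to missingness, which lowers them. I have not modelled either effect.

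**The case against.** **The documents do not say that people who know the arm score the answers.** A reader might infer it, since both people with access are, or very probably are, unmasked. It remains an inference: no section names the scorer, and the research associate's knowledge of the arm follows from assigned tasks rather than from any statement. This stands, and the finding is limited to an unnamed scorer and undescribed masking.

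**The shift is not shown to be as large as the target.** Three points exceed 2.39 (126%), so a reader might infer that scoring alone could produce the target difference. That would require identical content to score 0 in one arm and 1 in the other on at least 80% of open answers (2.39 / 3). In the example rule a full point needs a predefined keyword, so discretion lies mainly in the half-step. A half-step on every open answer gives 1.5 points, 63% of the target. This objection also stands.

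**Small shifts hardly matter.** True at the low end: 0.15 point raises the rate to only 5.4–6.1%. The documents give no rate of borderline answers, so the low end cannot be excluded.

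**The teaching pharmacist is kept away from the 1-month assessment.** Partly true: the Synopsis gives that contact to the research associate. But section 3.2 has completed questionnaires returned to the investigator, and collecting answers is not the same as scoring them.

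**Appendix 1 may already hold keyword lists.** Possible; it is not among the documents available here. A list would narrow the judgement on half-points without masking the scorer.

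**Conclusion.** The point holds in a limited form. Three of the 17 primary-endpoint points depend on judgement, the scorer is not named, and no masking is described. Under assumed shifts of 0.15–0.45 point, the 5% error rate becomes about 5–12% at 45 per group and about 6–15% at 62. A shift of 0.5 point gives about 9.5–14% and 11–18% respectively. These figures rest on the assumed share of answers moved, an SD between 2.67 and 3.78, and an unadjusted t-test.

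The trial is not invalidated: 14 of 17 points follow fixed rules. The gap should be closed before any free-text answer is scored, because doing so is inexpensive and the primary result would otherwise be hard to defend on this point.

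**What to change.** Add to section 3.2:

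1. After the last 1-month questionnaire is in, export the free-text answers without arm, time point or participant number. Give each answer a random linking code so that scores can be merged back for the ANCOVA. The key is kept by someone who does not score, for example the statistician or the pharmacist who already holds the randomization list.
2. Mix all patients and time points in random order and score them in one batch against a keyword list with half-point examples for all three items, fixed beforehand. First confirm whether Appendix 1 already contains this list.
3. Name the scorer, preferably the research associate rather than the teaching investigator.
4. Record telephone answers verbatim.

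Add to section 5.1 a supportive ANCOVA on the 14 closed items (maximum 14 points), adjusted for the baseline score on the same items. It shows whether the result depends on the judged items.

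**Cost.** A few hours of existing staff time and one extra analysis, with no change to sample size, visits or intervention. Final scores become available only at the end. Wording may still hint at the arm, a scorer may recognise some answers, and the recording of telephone answers stays unmasked.

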## 1 1 SYNOPSIS OF THE STUDY

Sponsor- Investigator	[name] University Hospitals of Geneva [name] [name] [contact]
Study Title	Disease and Medication Knowledge Improvement: A Swiss Single-center Randomized Controlled Trial With Heart Failure Inpatients
Short title / Study ID	Educ-IC 2022-00731
Protocol version and date	Version 2.0 (22.07.2022)
Study Registration	Intended for submission to the federal clinical trials database, Swiss National Clinical Trials Portal (SNCTP) and the international database, clinicaltrial.gov
Study category and Rationale	Clinical trials with interventions that are neither a therapeutic product nor a transplant, category A Other clinical trial according to ClinO, chapter 4
Background and Rationale	
People with heart failure are at risk of frequent hospitalization for cardiac decompensation. The stability of heart failure with reduced left ventricular ejection fraction (LVEF) is dependent on adequate and regular use of many medications. One reason for cardiac decompensation is poor medication adherence. To improve adherence, we would like to increase the knowledge of heart failure patients about their disease and their medication by conducting a therapeutic patient education (TPE) intervention.
 
This research project consists in setting up a pharmaceutical intervention with an educational aim for the patient during his hospitalization. The intervention consists of a therapeutic education interview conducted by a clinical pharmacist using playful tools adapted to the needs of heart failure patients. This intervention will take place at the hospitalized patient's bed. It will be associated with a preparation interview for the hospital discharge and a follow-up of the continuity of care during the week of the return home.

Risk/benefit assessment	The educational intervention of the pharmacist does not present any risk for the patient because it will not impact his medical management. It will be given in addition to the standard basic advice provided to patients and will provide them with quality medical information on heart failure (definition, symptoms, follow-up) and its treatments (indications, benefits, risks). It will allow the patient to be autonomous in monitoring the evolution of his disease and in the attitudes to adopt in case of aggravation of his disease.

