45 -20 to +20. A positive value means that the need for the treatment exceeds the concerns about  
46 taking it. This questionnaire has adequate internal consistency in a cardiac population  
47 (Cronbach alpha = 0.76) and correlates well with other measures of beliefs (57). The validated  
48 French version is used in this project. (62).

49  
50 **Medication adherence** will be assessed by means of a self-report questionnaire entitled  
51 "Three-item self-report scale (63). This questionnaire consists of 3 questions: one that  
52 evaluates the number of days that medication was forgotten in the last month, one that  
53 evaluates the frequency of taking medication as prescribed by the doctor, and the third that  
54 measures the patient's level of competence in taking medication correctly. Responses are

1 converted to a scale of 0 to 100 (0 being the lowest adherence and 100 the highest). An  
2 average of the three responses is used to assign the adherence score. This questionnaire has  
3 a high internal consistency (Cronbach alpha = 0.87) and correlates well with other measures  
4 of adherence (POC and MEMS). (63–65). We translated this questionnaire into French  
5 (Appendix 4) according to the methodology proposed by de Sousa et al. (66).  
6

7 Study participants' **satisfaction** will be assessed using a 13-question questionnaire (Appendix  
8 5) after the teaching interview to evaluate the usefulness and quality of the teaching service.  
9 A second satisfaction questionnaire consisting of 5 questions will be sent at 1 month after  
10 hospital discharge to assess the patient's overall satisfaction with the pharmacist's care  
11 (Appendix 6). These results will allow us to determine whether this new service should be  
12 continued and to identify its strengths and weaknesses.  
13

14 The patient's **experience and feelings** upon returning home will be assessed during a  
15 telephone call between D3 and D7 after the patient's discharge from the hospital. The objective  
16 will be to identify the patient's needs, their feelings about going home, what they liked, what  
17 they missed. It will also be assessed if the patient has obtained a treatment card, has organized  
18 to go and get his medication and has organized to integrate it into his daily life. A list of  
19 medications will be collected from the patient. The questions asked are presented in Appendix  
20 7.  
21

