- Clinical practice shows that many hospitalized patients with heart failure do not know what their disease is and how it is treated. A small field survey on the information needs of these patients was conducted with about ten patients in the General Internal Medicine Department of the HUG in 2021 and showed that patients were not able to define their heart failure disease, nor to explain the role of their medication and that they were eager to obtain more targeted information on their disease and their medication.

All hospitalized patients with left heart failure with a decreased LVEF  $\leq 40\%$  (HFrEF) as well as those with LVEF between 41 and 49% (HFmrEF) only if treated with heart failure specific drug therapy will be approached to introduce them to the study provided they meet the inclusion criteria.

The vast majority of the heart failure population is elderly and at risk for cognitive impairment. This may negatively influence the results of this score and bias the real impact of the educational intervention. To address this issue, only patients without cognitive impairment will be included. To identify the cognitive status of each patient, the following items will be analyzed in order of priority.

- Judgment of the internal physician in charge of the patient.

- If the physician is in doubt about the patient's cognitive status, a Mini Mental Status (MMS) and a clock test (only if the MMS is greater than 24) will be performed by the investigator or a geriatric liaison nurse attached to the General Internal Medicine Service. Cognitive impairment is possible if MMS score  $\leq 24$  and if MMS  $\geq 24$  and clock test score  $\leq 7$ .

Patients hospitalized at the University Hospital of Geneva meeting the following inclusion criteria are eligible for the study:

- Hospitalized in the Department of General Internal Medicine or Cardiology for decompensated heart failure (also called cardiac decompensation, acute heart failure)
  - o with lowered left ventricular ejection fraction (LVEF) ( $\leq 40\%$ ) of any origin;
  - o with slightly reduced left ventricular ejection fraction (LVEF) (41-49%) only if treated with the specific drug therapy for heart failure

Or

- Hospitalized in the Department of General Internal Medicine or Cardiology and presenting during hospitalization with decompensated heart failure (also called cardiac decompensation, acute heart failure)

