Vital parameters data			
39	Heart rate (admission)	Medical record	Number (bpm) and date: .....bpm (...../...../.....)
40	Systolic blood pressure (admission)	Medical record	Number (mmHg) and date: .....mmHg (...../...../.....)

41	Diastolic blood pressure (admission)	Medical record	Number (mmHg) and date: .....mmHg (...../...../.....)
42	Weight (admitted)	Medical record	Number (kg) and date : .....kg (...../...../.....)
43	Weight (exit)	Medical record	Number (kg) and date : .....kg (...../...../.....)
44	Body mass index (Kg/m  )	Medical record	 <18  18-24.9  25-29.9  30-34.9  35-39.9  ≥40 
Drug Data			
45	Medication at home before admission	Medical record	Date: (...../...../.....)  Specialty / INN / Dosage / Dosage e.g. Forxiga, dapagliflozin, 10mg, i.d
46	Number of medications before hospitalization	Medical record/patient interview/	 0  1-2  3-4  >4
47	Number of heart failure medications prior to hospitalization	Medical record/patient interview/	 0  1  2  3  4  5  >5

48	Heart failure medication list (home)	Medical record	 Diuretic  Beta-blocker  IECA/ARA  ARNI  Aldosterone antagonist (ARM)  SGLT2 inhibitor  Ivabradine  Digoxin  Vericiguat
49	Heart failure medication list (hospitalization)	Medical record	 Diuretic  Beta-blocker  IECA/ARA  ARNI  Aldosterone antagonist (ARM)  SGLT2 inhibitor  Ivabradine  Digoxin  Vericiguat

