#### Assessment of therapeutic adherence (secondary outcome)

Adherence to therapy will be assessed for all participants with the 3-item self-report questionnaire (Appendix 4) on two occasions. It will be presented to the participant by the investigator at time 0 after obtaining the consent form (pre-test), as well as at 1 month post-hospitalization. During hospitalization, the questionnaire will be sent to the patient by the investigating pharmacist and completed by the patient himself with the help of the pharmacist if necessary.

At 1 month after discharge, the questionnaire will be sent to the patient by email or post. If no return is obtained, the research assistant will address the questionnaires to them during a phone call.

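### The before/after change in beliefs and adherence in the intervention arm alone should give way to a baseline-adjusted comparison with the controls

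*Combined protocol and SAP*

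**What the plan says.** Section 3.2 of the protocol gives two versions of the belief and adherence endpoint. The controlled one comes first: "Secondary endpoints included differences in medication belief and adherence scores and the" rate of unplanned care, compared between the two groups at 1 month. The second is confined to one arm: "They also focused, for the intervention group, on the difference in belief and therapeutic" "adherence scores between the period before the educational intervention during" the hospital stay and the period after it, that is, 1 month after discharge.

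The starting point is an acute admission. The first inclusion route in section 4.1 is "Hospitalized in the Department of General Internal Medicine or Cardiology for decompensated heart failure", and the second is decompensation arising during a stay. The Synopsis states that "One reason for cardiac decompensation is poor medication adherence". Table 2, item 31, offers poor adherence as one of 15 possible causes of the acute episode.

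Controls are measured too. On adherence, section 4.3 says of the questionnaire, for all participants: "It will be presented to the participant by the investigator at time 0 after obtaining the consent form (pre-test), as well as at 1 month". The section on beliefs gives the same two time points in both groups.

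For continuous secondary outcomes, the introduction to section 5 and Secondary analyses in section 5.1 specify Student's t tests between the randomised groups. Neither mentions a paired or within-arm test. Only the knowledge score is adjusted for its baseline (section 5.1, Primary analysis).

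**The concern.** A change within one arm adds together the effect of teaching and everything else that happens between the ward and 1 month after discharge. At least two other influences are visible in the documents.

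- **Selection at a low point.** Some patients are admitted because their adherence was poor, so part of the sample enters when adherence is unusually low. A rise would be expected under usual care (regression to the mean).
- **Treatment change.** Section 4.1 expects newer first-line drugs to alter prescribing, and Table 2 records heart failure drugs separately at home, in hospital and at discharge (items 48 to 50). The regimen at 1 month may differ from the one the pre-test describes.

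Both act in controls as well, so the randomised comparison removes them and the intervention-only change does not. Section 7.1 says that improvement in knowledge, beliefs and adherence could lead to the interviews being offered to all heart failure patients in the hospital. It does not say whether improvement means relative to controls or relative to the patient's own pre-test. With two endpoints for the same outcome and no rule on which governs, a favourable before/after change could be reported beside an inconclusive comparison with controls.

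**Working it through.** **Figures in the plan.** There is none to reproduce: the documents give no SD, expected change or before/after correlation for the belief or adherence scores. The only inputs taken from them are the 5% two-sided level and the group sizes in section 5.1: 45 per arm enrolled, about 40 after 10% loss, and 62 per arm expected. Drift d (in SD units) and correlation r are assumptions, so the results show a range and are not a forecast. The paired test is also an assumption, since the plan contains none.

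**Step 1. Paired test in one arm with no teaching effect.** Let every patient drift by d between pre-test and 1 month, with equal variances. The change has SD √(2(1 − r)), so the noncentrality is d√n / √(2(1 − r)), on n − 1 degrees of freedom.

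For n = 45 and r = 0.5, √(2 × 0.5) = 1 and √45 = 6.708:

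- d = 0.25: noncentrality 0.25 × 6.708 = 1.677; rejection rate 0.375.
- d = 0.5: noncentrality 0.5 × 6.708 = 3.354; rejection rate 0.907.

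| n (pairs) | r | d = 0.25 | d = 0.5 |
|---|---|---|---|
| 40 | 0.5 | 0.338 | 0.869 |
| 45 | 0.3 | 0.284 | 0.792 |
| 45 | 0.5 | 0.375 | 0.907 |
| 45 | 0.7 | 0.563 | 0.989 |
| 62 | 0.5 | 0.491 | 0.972 |

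With no drift the rate is 0.05 throughout. With a drift of 0.1 SD at n = 45 it is 0.086 to 0.135 over r = 0.3 to 0.7.

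**Step 2. Between-arm comparison of the same data.** Simulation used 45 per arm, r = 0.5, the same drift in both arms and no teaching effect (20,000 runs; 4,000 for ANCOVA).

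| Drift | Paired, one arm | t test at 1 month | t test on change | ANCOVA |
|---|---|---|---|---|
| 0.3 SD | 0.505 | 0.050 | 0.053 | 0.045 |
| 0.5 SD | 0.905 | 0.050 | 0.049 | 0.046 |

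A significant within-arm change beside a non-significant 1-month t test occurred in 48% of runs at 0.3 SD and 86% at 0.5 SD.

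**Step 3. Which controlled analysis.** Relative to the variance of the 1-month score (1.00 for the planned unadjusted t test), the residual variance is 1 − r² for ANCOVA and 2(1 − r) for a change score:

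| r | ANCOVA | Change score |
|---|---|---|
| 0.3 | 0.91 | 1.40 |
| 0.5 | 0.75 | 1.00 |
| 0.7 | 0.51 | 0.60 |

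ANCOVA is more precise than the planned test at all three correlations. A change score is less precise than the planned test when r is below 0.5.

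**The case against.** The strongest reply is that the secondary objective already has a controlled analysis. The between-group comparison is listed first in section 3.2, the same section says the control group is there to show the real effect of teaching, and section 5 plans only between-group tests. This stands. A reader might infer that the plan rests its adherence and belief claims on the uncontrolled change, or that recovery will inevitably be reported as an effect. The documents do not support either. They show a declared endpoint with no stated analysis or interpretation, which can mislead but need not.

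Three further limits stand.

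- The rejection rates describe a test that is not planned, under assumed drift. They show how an uncontrolled change behaves and do not give the error rate of this trial.
- The evidence for a low starting point concerns adherence only. Nothing shows that beliefs are shifted at decompensation or in which direction they would move. The share of patients admitted because of poor adherence is not given either.
- A reader might also infer that the adherence pre-test is invalid for patients with no earlier heart failure treatment. Such patients appear eligible: the requirement of at least two heart failure drugs need not predate admission, and item 47, "Number of heart failure medications prior to hospitalization", allows zero. But section 3.2 describes an item that "evaluates the number of days that medication was forgotten in the last month", without restricting it to heart failure drugs, and the full wording is in Appendix 4, which is not available here. If the scale covers all medication, a patient on other home drugs has a usable baseline. The number of such patients is unknown.

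None of this turns the within-arm change into evidence of effect.

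**Conclusion.** The point holds in a limited form. Section 3.2 makes an intervention-only before/after change a secondary endpoint, although the same data exist for controls. That change cannot separate teaching from recovery, regression to the mean or altered treatment. The risk is best supported for adherence and remains open for beliefs. The illustrative range of about 37% to 91% depends on 45 complete pairs, a drift of 0.25 to 0.5 SD, r = 0.5 and a paired test being run; over r = 0.3 to 0.7 it widens to 28% to 99%. Whatever the true drift, provided it is common to both arms, the randomised comparison stays near 5%.

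The primary endpoint is not affected, and the planned between-group comparison of these outcomes remains valid. Adjusting that comparison for baseline is a gain in precision and does not correct an error.

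**What to change.** 1. In section 3.2, remove the intervention-only change as an effect endpoint. Define the effect on beliefs and on adherence as the between-arm difference at 1 month adjusted for the pre-test score.
2. In section 5 and in Secondary analyses (section 5.1), replace the unadjusted t test for these two outcomes by the ANCOVA already planned for knowledge. Amend the matching Synopsis text.
3. Report within-arm changes for both arms side by side, as descriptive summaries without a test.
4. If Appendix 4 asks specifically about heart failure medication, add a sensitivity analysis of adherence limited, in both arms, to patients with at least one heart failure drug before admission (item 47 of 1 or more). This is a pre-admission characteristic, so the filter keeps the randomised comparison. Leave the recall period of the published scale as it is; the available evidence does not justify rewording it.

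No new data are needed, since the control pre-test and 1-month values are already collected. The cost is a change of wording and slightly more analysis work.
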